8.1 Handling of missing data and outliers

No imputation of missing data will be performed.

8.2 Multicenter studies

Not applicable. This observational study was conducted in one site.

8.3 Multiple comparisons and multiplicity

No comparison and multiplicity adjustment will be performed, only descriptive statistics.

8.4 Derived and computed variables

8.4.1 Age

Age at informed consent (years) will be calculated as:

$$\text{Age (years)} = \frac{\text{Date of informed consent} - \text{Date of birth}}{365.25}$$

Age at diagnosis of malignancy (years) will be calculated as:

$$\text{Age at diag. of malignancy (years)} = \frac{\text{Date of diagnosis of malignancy} - \text{Date of birth}}{365.25}$$

Age at HLH diagnosis (years) will be calculated as:

$$\text{Age at HLH diag. (years)} = \frac{\text{Date of HLH diagnosis} - \text{Date of birth}}{365.25}$$

Ages will be rounded to the closest whole year for presentation in the summary tables and listings.

8.4.2 LLOQ and ULOQ

Values reported as below the lower limit of quantification (LLOQ) will be replaced by LLOQ/2 and values above upper limit of quantification (ULOQ) will be replaced by ULOQ prior to the statistical analyses.

9 Patient disposition

Not applicable, all patients who signed an ICF will be enrolled in the study. No study treatment is given.

10 Demographics and baseline characteristics

10.1 Demographics

Demographic characteristics will be summarized by HLH patients, non-HLH patients and overall for the All enrolled set:

- Age (years) at ICF
- Sex: Male, Female
- Weight (kg) at ICF
- Height (cm) at ICF

Demographic data will also be listed.

10.2 Medical History

Medical History characteristics (malignancy and HLH) will be summarized by HLH patients, non-HLH patients and overall, for the All enrolled set and will include:

- Malignancy
 - Age at diagnosis of malignancy (years)
 - Type of malignancy
 - Type of malignancy will be listed as entered in the CRF and summarized as coded.
- HLH (only applicable to the HLH patients)
 - Age at HLH diagnosis (years)
 - Chemotherapy induced malignancy: Yes, No, Not Tested
 - Molecular diagnosis relevant for HLH: Yes, No, Not Tested

- Mutation (if molecular diagnosis): Homozygous, Heterozygous
- Mutation (if molecular diagnosis): PRF1, UNC13D, STX11, RAB27A, STXBP2, SH2D1A, LYST
- Infectious trigger detected: Yes, No, Not Tested
Note: type and subtype if available, e.g. Virus (EBV, CMV, ...), fungi, bacteria will be listed.
- HLH 2004 criteria that were met
 - Fever: Yes, No
 - Splenomegaly: Yes, No
 - Hb <90 g/L: Yes, No, Not Applicable
 - Platelets <100*10⁹/L: Yes, No, Not Applicable
 - Neutrophils <1*10⁹/L: Yes, No, Not Applicable
 - Hypofibrinogenaemia: Yes, No, Not Tested
 - Hypertriglyceridaemia: Yes, No, Not Tested
 - Increased level of sCD25: Yes, No, Not Tested
 - Evidence of haemophagocytosis: Yes, No, Not Tested
 - Decreased or absent NK cell cytotoxicity: Yes, No, Not Tested
 - Additional supportive evidence: CNS involvement, Hepatomegaly

Medical History Characteristics data will also be listed.

No medical history apart from HLH and malignancy is collected.

[figure not shown]
11 Prior and concomitant medication

Prior and concomitant medications are collected as free text and will not be coded and summarized, only listed as entered in the CRF.

12 Endpoint analyses

12.1 Inflammatory biomarkers

The inflammatory biomarkers as listed in section 3.2.1 will be displayed in scatter plots grouped by HLH and non-HLH group as in the below example.

For the HLH group the biomarker value closest to the date of HLH diagnosis (value must be after HLH diagnosis) will be used if more than one sample is available. For the non-HLH group the minimum and maximum value will be used and displayed in different colours/markers. If just one value available that value will be displayed with the same colour/marker as the HLH group. Biomarker data will be summarized by group using descriptive statistics and presented for HLH patients, non-HLH patients and overall.

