and disease activity and prognosis during the M-HLH course. Inflammatory markers will also be measured in a group of control patients diagnosed with hematological malignancy in absence of HLH (as described above).

Data collection may be performed retrospectively if sufficient clinical information is available to allow for a meaningful interpretation of the biomarker results.

An approximate volume of 500 µl – 1 ml of serum or plasma is required per time point. Whenever possible, serum (and not plasma) should be collected, as this is the preferred matrix for the biomarker analysis.

In addition to the serum samples for the biomarker analysis, relevant information gathered by the treating physician will be collected in a data collection form. This will include information on the clinical presentation of M-HLH, the type of underlying malignancy, the date of onset of malignancy in relation to HLH manifestations, treatment regimen prior to and/or ongoing at the time of M-HLH onset, laboratory parameters, M-HLH disease activity (e.g. newly diagnosed, reactivation), specific HLH therapy with best response to the therapy, other concomitant medications, patient follow-up and disposition, stem cell transplant status, duration of response, and survival. Whenever possible, collection of serum samples for biomarker analysis and relevant information should occur at M-HLH diagnosis, at regular time intervals during the treatment course, at resolution and/or reactivation of the disease.

In addition to the above a minimum of 1 ml of whole blood will be collected (EDTA tubes) for genetic characterization and identification of the presence of genetic variants of the genes typically causing primary HLH. A specific consent for genetic testing must be given by the patient. Genetic samples may also be collected from existing bank of samples (frozen whole blood in EDTA or frozen extracted DNA), if proper consent has been obtained.

---

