**Statistical Analysis:**

All analyses are exploratory. Statistical analyses of the data collected in this study will be focused on providing tabular and graphical summaries of the levels of inflammatory markers and of the clinical features of the disease both at diagnosis and during the course of treatment. Levels of inflammatory markers will be compared between patients with active M-HLH and the control group (i.e. hematological malignancy in absence of HLH). In addition, the degree of correlation between inflammatory markers, and between inflammatory markers and the severity of clinical manifestations, response to therapy, and survival of the patients will be assessed. Analyses may also be performed to study these relationships in various subgroups of patients, depending on the demographic, genetic and clinical characteristics observed, including *a posteriori* diagnosis based on HLH-2004 diagnostic criteria (Henter et al., 2007).

Criteria for diagnosis are:

- i) Fever
- ii) Splenomegaly
- iii) Cytopenia (affecting  $\geq 2$  of 3 lineages in peripheral blood):
  - Hb  $<90$  g/L (in infants  $< 4$  weeks: Hb  $<100$  g/L)
  - Platelets  $<100 \times 10^9$ /L
  - Neutrophils  $<1.0 \times 10^9$ /L
- iv) Hypertriglyceridemia and/or hypofibrinogenemia: Fasting triglycerides  $\geq 3.0$  mmol/L; Fibrinogen  $\leq 1.5$  g/L
- v) Hemophagocytosis in bone marrow or other specimens
- vi) Low or absence NK-cell activity (according to local laboratory reference)
- vii) Ferritin  $\geq 500$   $\mu$ g/L
- viii) sCD25  $\geq 2400$ U/ml

---

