12.2 Inflammatory biomarkers - correlations

The degree of correlations between inflammatory markers and between inflammatory markers and laboratory assessments (potential markers of disease activity) will be assessed.

The correlations to be performed are:

1. All inflammatory biomarkers vs. all other inflammatory biomarkers as listed in section 3.2.1
2. Biomarkers relevant for emapalumab (i.e. CXCL9, CXCL10, IFN γ and sIL2R α) vs. all laboratory assessments as listed in section 3.2.2

The correlations will be evaluated by plotting biomarker scores i.e., CXCL9 vs. CXCL10 (for all combinations) in scatter plots. In the scatter plots the groups (HLH and non-HLH) will be represented by different colors. The biomarker value closest to the date of HLH diagnosis will be used if more than one sample available. For the non-HLH group the minimum and maximum value will be displayed with different markers. If just one value available that value will be displayed with another marker.

Data will be investigated to confirm normal or log-normal distribution of the parameters. If normal, the actual values will be plotted. If not normal, log-transformed values will be plotted.

The correlated samples should be within a time frame of three days.

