13.2 Laboratory data

A subset of the laboratory data collected will be displayed in scatter plots the same way as the biomarker data described in section 12.1 grouped by HLH and non-HLH group. The lab data to be plotted are:

- AST, ALT, Alkaline Phosphatase
- Total and conjugated Bilirubin
- CRP
- D-dimers
- white blood cells and differential count, platelets
- Ferritin
- Fibrinogen
- Lactate dehydrogenase

For the HLH group the value closest to the date of HLH diagnosis (value must be after HLH diagnosis) will be used if more than one sample is available. For the non-HLH group the minimum and maximum value will be displayed in different colours/markers. If just one value available that value will be displayed with the same colour/marker as the HLH group.

Laboratory data will be summarized by group using descriptive statistics and presented for HLH patients, non-HLH patients and overall.

All laboratory data will be listed by patient.

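### SAP 12.1 and 13.2 choose the HLH-group value by date alone, so a resolved-disease sample can enter, unmarked, what the protocol set up as an active M-HLH contrast

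*SAP*

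**What the plan says.** - **Comparison.** Protocol, Statistical Analysis: "Levels of inflammatory markers will be compared between patients with active M-HLH and the control group", the controls being patients with a hematological malignancy and no HLH.
- **Sampling.** Protocol, Study Design, repeated in SAP 4.1, asks for samples, where possible, "at M-HLH diagnosis, at regular time intervals during the treatment course, at resolution and/or reactivation of the disease". Retrospective collection is allowed if there is enough clinical information to interpret the results.
- **Activity.** The same section lists, among the items on the data collection form, "M-HLH disease activity (e.g. newly diagnosed, reactivation". These are examples. The text does not say that status is recorded for each sample.
- **Selection for biomarkers.** SAP 12.1, on HLH patients: "the biomarker value closest to the date of HLH diagnosis (value must be after HLH diagnosis) will be used if more than one sample" exists.
- **Selection for laboratory data.** SAP 13.2: "For the HLH group the value closest to the date of HLH diagnosis (value must be after HLH diagnosis) will be used", again where there is more than one sample.
- **Selection for correlations.** SAP 12.2: "The biomarker value closest to the date of HLH diagnosis will be used if more than one sample available". The condition that the value follow diagnosis is not repeated. A separate sentence adds: "The correlated samples should be within a time frame of three days".
- **Splits and disclosed changes.** SAP 12.4 separates HLH from non-HLH and nothing further. SAP 14 lists the missing CXCL11, IL-17 and genetic data as changes from the protocol, and no others.

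**The concern.** The study asks whether IFNγ and the chemokines it induces track M-HLH activity. The protocol therefore restricts the HLH side of the group contrast to active disease. The SAP drops that restriction: it takes one value per HLH patient by its distance from the diagnosis date and does not ask what state the disease was in when the sample was drawn.

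Because the protocol deliberately collects samples at resolution, some values in the data may come from disease that has settled. If one of these is the closest eligible value, it represents the patient in the HLH group and looks the same as a value from active disease. If markers fall at resolution, the HLH levels move towards control and the contrast is understated. The reader of the plots or summaries cannot see that this has happened, and SAP 14 does not report that the active condition was lost.

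**Working it through.** **1. The passages side by side**

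| Element | Protocol | SAP |
|---|---|---|
| HLH side of the contrast | Active M-HLH | HLH group, no activity condition (12.1, 13.2) |
| Samples in the data | Diagnosis, treatment, resolution, reactivation | Same text (4.1) |
| Choice among samples | Not specified | Closest to, and after, diagnosis (12.1, 13.2) |
| Maximum interval from diagnosis | None | None |
| Departure listed in SAP 14 | – | No |

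The three-day window in 12.2 ties the two correlated samples to each other. It does not limit how far either lies from diagnosis. In 12.1 and 13.2 the selection applies when there is more than one sample, so a lone sample is used whatever its timing.

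**2. The 12.1 rule applied to example schedules**

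Days are counted from diagnosis. All schedules are assumed; the documents give no sample timings.

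| Samples available | Chosen if after means later than day 0 | Chosen if day 0 counts |
|---|---|---|
| Day 1 near diagnosis, day 40 resolution, day 90 reactivation | Day 1 | Day 1 |
| Day 0 diagnosis, day 7 treatment, day 40 resolution, day 90 reactivation | Day 7 treatment | Day 0 diagnosis |
| Day 0 diagnosis, day 40 resolution, day 90 reactivation | Day 40 resolution | Day 0 diagnosis |
| Day 40 resolution, day 90 reactivation | Day 40 resolution | Day 40 resolution |
| Day 40 resolution only | Day 40 resolution | Day 40 resolution |

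The rule works in the first two rows. It picks resolved disease in the last two, and in the third if a same-day sample is excluded. The SAP does not say whether day 0 is eligible.

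**3. Possible size**

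The plan gives no figure to reproduce. The HLH group size is 19 (SAP section 6). Two quantities must be assumed: k, the number of HLH patients represented by a resolved-disease value, and r, the ratio of active to resolved level. Suppose these k patients would otherwise have been at the group's average active level.

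- Arithmetic mean as a share of the all-active mean: 1 − (k/19) × (1 − 1/r).
- Geometric mean as a share of the all-active value: r^(−k/19). This is the mean on the log scale, which 12.2 uses for plots when values are not normal.

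Example, k = 3 and r = 5: arithmetic 1 − (3/19) × 0.8 = 0.87; geometric 5^(−3/19) = 0.78.

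| r | Arithmetic, k = 1 / 3 / 5 | Geometric, k = 1 / 3 / 5 |
|---|---|---|
| 2 | 0.97 / 0.92 / 0.87 | 0.96 / 0.90 / 0.83 |
| 5 | 0.96 / 0.87 / 0.79 | 0.92 / 0.78 / 0.65 |
| 10 | 0.95 / 0.86 / 0.76 | 0.89 / 0.70 / 0.55 |

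The effect on the planned median and quartiles depends on the distribution of values and cannot be worked out from the documents.

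**The case against.** **The rule is usually sensible.** Any sample soon after diagnosis is chosen first, and the protocol asks for samples at diagnosis and regularly during treatment. This stands: the fault is confined to patients without such a sample. A date rule is also objective and easy to reproduce, which is a reason to keep it as the basis.

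**The failing sample sets may be rare.** A reader might infer from the allowance for retrospective collection that they are likely. The documents do not support that: they give no sample timings, and they require enough clinical information for interpretation. In the adult series cited in the protocol's background, median survival was 1.5 months and 31% were alive at 6 months, so a late resolution followed by a reactivation would be uncommon there; in the paediatric series, 6-month survival was 63% to 67%. Frequency is therefore unknown. A lone resolution sample, however, needs no later reactivation to cause the problem.

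**Patients who enter at reactivation.** A reader might infer that the rule misplaces them by anchoring to an earlier episode. It does not. If sampling starts at reactivation, the closest value after an earlier diagnosis is the first reactivation sample. Nor does the SAP say first diagnosis; it refers only to the date of HLH diagnosis.

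**The correlation plots.** A reader might infer that 12.2 should also be limited to active disease. That would work against the second objective, which relates markers to disease activity and needs samples over a range of activity. Labelling the points is enough.

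**Selecting on activity has its own bias.** Activity is judged by the treating physician, and sCD25 is both an HLH-2004 criterion and an analysed marker. Selection on judged activity could inflate the contrast for sCD25 and for markers correlated with it. This stands as a cost, and is a reason to show results with and without the excluded patients.

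**Nothing is tested.** SAP section 8 plans description only, and all patient data are listed. So no error rate is at risk. But description is the whole output, SAP section 2 allows it to enter submissions and manuscripts, and listings do not correct a summary or a plot.

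**Conclusion.** The point holds in a limited form. SAP 12.1 and 13.2 replace the protocol's active M-HLH contrast with a date rule that has no activity condition and no maximum interval, and SAP 14 does not say so. A resolved-disease value can therefore stand unmarked in the HLH group when no eligible sample lies between diagnosis and resolution, or when the only sample is a resolution sample.

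The direction, towards control, assumes that markers fall at resolution. The size rests entirely on k and r, neither of which is in the documents. Over the range shown, the HLH mean would be 0.76 to 0.97 of its all-active value, and the geometric mean 0.55 to 0.96. With no affected patients there is no effect. These figures must not be read as an estimate of bias in this study.

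For 12.1 there is one further assumption: the selection rule is written beside the plots, and the later sentence on descriptive summaries does not repeat it. That it governs the summaries too is the natural reading, but it is an inference.

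**What to change.** - **12.1 and 13.2.** Keep the closest-to-diagnosis rule, but apply it among samples taken before documented resolution or during a reactivation. State that a sample on the day of diagnosis is eligible, and that the same selection governs both plots and summaries.
- **Patients with only resolution-phase samples.** Plot them with a separate marker and leave them out of the active M-HLH summary, or give that summary with and without them.
- **12.2.** Keep all samples and mark each point by disease status at sampling. Exclude none on the ground of status.
- **Derivation.** State how status at sampling is obtained from the form data. The documents do not show a status field for each sample or an onset date for each episode, so the rule should not depend on these unless they exist.
- **Section 14.** List whatever departure from the protocol's active comparison remains.

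The cost is SAP wording, a derived status variable and a plot marker; no new data collection is proposed. A few patients may leave the active-disease summary in a group of 19, and status will depend on the treating physician's record.

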12.2 Inflammatory biomarkers - correlations

The degree of correlations between inflammatory markers and between inflammatory markers and laboratory assessments (potential markers of disease activity) will be assessed.

The correlations to be performed are:

1. All inflammatory biomarkers vs. all other inflammatory biomarkers as listed in section 3.2.1
2. Biomarkers relevant for emapalumab (i.e. CXCL9, CXCL10, IFN γ and sIL2R α) vs. all laboratory assessments as listed in section 3.2.2

The correlations will be evaluated by plotting biomarker scores i.e., CXCL9 vs. CXCL10 (for all combinations) in scatter plots. In the scatter plots the groups (HLH and non-HLH) will be represented by different colors. The biomarker value closest to the date of HLH diagnosis will be used if more than one sample available. For the non-HLH group the minimum and maximum value will be displayed with different markers. If just one value available that value will be displayed with another marker.

Data will be investigated to confirm normal or log-normal distribution of the parameters. If normal, the actual values will be plotted. If not normal, log-transformed values will be plotted.

The correlated samples should be within a time frame of three days.

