2. Primary and secondary HLH patients have hypercytokinemia with elevated levels of several pro-inflammatory cytokines including IFN $\gamma$  (Henter et al., 1991; Janka et al., 1998; Xu et al. 2012). More recently, high levels of IFN $\gamma$  were demonstrated both in patients with HLH secondary to infections and in sJIA patient developing MAS (Buatois et al., manuscript

submitted; Bracaglia et al. manuscript submitted). The levels of CXCL9, CXCL10 and CXCL11, three chemokines known to be induced by IFN $\gamma$ , were also significantly elevated. Noteworthy, levels of IFN $\gamma$  and of the three IFN $\gamma$ -inducible chemokines were found to significantly correlate with laboratory parameters of disease severity, such as ferritin, platelet count and transaminases.

3. A Phase 2 pilot study is presently ongoing to evaluate the efficacy and safety of treatment with NI-0501, an anti-IFN $\gamma$  monoclonal antibody, in pHLH. Based on data gathered so far, NI-0501 treatment has been well tolerated and shown a favorable impact on all relevant clinical and laboratory features of HLH such as fever, splenomegaly, cytopenia, hyperferritinemia, hypofibrinogenemia, and also CNS signs/symptoms (Jordan et al, 2015).

No animal models specific to M-HLH have been described (Brisse et al., 2015). The levels of IFN $\gamma$  and other pro-inflammatory cytokines at diagnosis and their correlation with clinical evolution and severity of the HLH manifestations during and after therapy have been poorly characterized for M-HLH. The fact that primary HLH and HLH secondary to inflammatory/autoimmune diseases or infections have many pathophysiological and clinical features in common with M-HLH, suggests that IFN $\gamma$  might also play a key role in M-HLH. The present observational study is designed to provide a better understanding of the potential use of IFN $\gamma$  and IFN $\gamma$ -inducible chemokines as markers of M-HLH disease activity and potential prognosis and of the possible role of IFN $\gamma$  as a therapeutic target in M-HLH, and to explore the genetic profiles in patients with M-HLH with regard to HLH-related genes.

---

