Study Objectives:	

• To determine the levels of inflammatory markers including, but not limited to interferon gamma (IFN<math>\gamma</math>), interleukin 1 beta (IL-1<math>\beta</math>), interleukin 6 (IL-6), interleukin 10 (IL-10), interleukin 17 (IL-17), soluble IL-2 Receptor <math>\alpha</math> (sCD25), C-X-C chemokine ligand 9 (CXCL9), C-X-C chemokine ligand 10 (CXCL10), C-X-C chemokine ligand 11 (CXCL11), soluble CD163 (sCD163), neopterin and Tumor Necrosis Factor alpha (TNF<math>\alpha</math>) in patients diagnosed with M-HLH and whenever possible, to monitor the evolution over time of these markers.

• To assess the relationship between the above mentioned inflammatory cytokines and disease activity.

• To assess the relationship between genetic variants of the genes typically causing primary HLH and M-HLH and associated inflammatory markers.

Sample Size:	A minimum of 14 (maximum of 50) M-HLH patients will be studied, including a minimum of 7 non iatrogenic M-HLH and 7 iatrogenic M-HLH. A control group of 10 patients with a diagnosis of hematological malignancy in absence of HLH will also be evaluated.
Study Population:	
Male and female (adult and children) patients who are diagnosed with M-HLH and that meet the inclusion criteria listed below.
 
In addition, patients with a diagnosis of hematological malignancy in the absence of HLH will be included as a control group.

Inclusion Criteria:	

1. Patients diagnosed with HLH in the context of a malignancy. The diagnosis of M-HLH will be established by the treating physician.

2. The patient or patient's legal representative (in case the patient is < 18 years old) must have consented to the use of their clinical data for research purposes at the site.

3. For the control group, patients with a diagnosis of hematological malignancy and never diagnosed with HLH or no suspicion of HLH (at any time, including time after sample collection in case of use of retrospective sample).

Study Design:	This is a non-interventional study designed to determine the levels of pro-inflammatory markers (as listed above) in patients diagnosed with M-HLH and to assess the relationship between the biomarkers

---

Protocol NI-0501-07 version 1.0, dated 12 Feb 2016

---

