3.1 Study objectives

- To determine the levels of inflammatory markers including, but not limited to interferon gamma (IFN γ), interleukin 1 beta (IL1 β), interleukin 6 (IL-6), interleukin 10 (IL-10), interleukin 17 (IL-17), soluble IL-2 Receptor α (sCD25), C-X-C chemokine ligand 9 (CXCL9), C-X-C chemokine ligand 10 (CXCL10), C-XC chemokine ligand 11 (CXCL11), soluble CD163 (sCD163), neopterin and Tumor Necrosis Factor alpha (TNF α) in patients diagnosed with M-HLH and whenever possible, to monitor the evolution over time of these markers.
- To assess the relationship between the above-mentioned inflammatory cytokines and disease activity.
- To assess the relationship between genetic variants of the genes typically causing primary HLH and M-HLH and associated inflammatory markers.

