3.2 Study endpoints

3.2.1 Inflammatory biomarkers

Level of

- CXCL10 (pg/mL)
- CXCL9 (pg/mL)
- IFNg V-PLEX (pg/mL)
- IL10 V-PLEX (pg/mL)
- IL1B V-PLEX (pg/mL)
- IL6 V-PLEX (pg/mL)
- Neopterin (nM)
- TNFa V-PLEX (pg/mL)
- Total hIFN γ (pg/mL)
- sCD163 (ng/mL)

- sIL2R α (pg/mL), also called sCD25

Note: No data reported for C-XC chemokine ligand 11 (CXCL11) and interleukin 17 (IL-17).

The biomarkers are measured in the M-HLH group and in the malignant control group without M-HLH.

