13.3 Vital signs

Weight and Height are only collected at screening/ICF. They will be presented as part of the Demographic table (see Section 10.1).

14 Changes from the planned analyses in the clinical trial protocol

No data reported for C-XC chemokine ligand 11 (CXCL11) and interleukin 17 (IL-17), hence no analyses performed for these biomarkers.

Genetic information was only obtained from 5 out of 19 HLH patients, no analysis on genetic variants will be performed.

15 References

N/A

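### SAP 12.2 plots only four of the ten measured analytes against laboratory disease activity, so objective 2 goes unanswered on those measures for the other six

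*SAP*

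**What the plan says.** SAP 3.1 keeps the protocol's second objective unchanged: "To assess the relationship between the above-mentioned inflammatory cytokines and disease activity". It refers back to the whole marker list of the first objective and names no subset. The protocol's Study Objectives likewise speak of "inflammatory cytokines and disease activity" without a restriction, and its Exploratory Parameters section heads the whole panel as markers of disease activity. The protocol's Statistical Analysis section adds that the correlation "between inflammatory markers and the severity of clinical manifestations, response to therapy, and survival of the patients will be assessed".

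SAP 3.2.1 lists 11 assays. IFNγ appears twice, as V-PLEX and as total. CXCL11 and IL-17 are noted as having no data. For the rest, "The biomarkers are measured in the M-HLH group and in the malignant control group without M-HLH".

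SAP 3.2.2 says that selected markers will be related to laboratory markers of disease activity, without naming the selection or giving a reason. SAP 12.2 opens by relating inflammatory markers in general to laboratory assessments. Its list of correlations to be performed then sets all markers against each other (item 1), but against the laboratory list only "Biomarkers relevant for emapalumab (i.e. CXCL9, CXCL10, IFN γ and sIL2R α) vs. all laboratory assessments" (item 2).

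SAP section 14 records two changes from the protocol: the missing CXCL11 and IL-17 data, and "Genetic information was only obtained from 5 out of 19 HLH patients, no analysis on genetic variants will be performed".

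**The concern.** Laboratory assessments are the disease-activity measure in the SAP's correlation analysis. A marker left out of item 2 is not related to any of them, although the objective names it and its data exist. No other SAP analysis fills the gap, because none relates any marker to clinical severity, response or survival.

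The stated purpose (Protocol Background; SAP section 2) includes the possible role of IFNγ as a therapeutic target, and SAP section 2 says that the results could go into regulatory submissions or manuscripts. A plot of CXCL9 against ferritin is hard to interpret alone. If IL-6 or TNFα follows ferritin in the same way, the reader should be able to see it. The protocol itself makes these natural comparators, since its Background names TNFα, IL-6 and IL-10 among the cytokines raised in secondary HLH. Section 14 also does not tell a reader of the results that objective 2 was narrowed.

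**Working it through.** The plan states no sample-size, power or precision figure to reproduce. The check is a count, followed by a look at what 19 patients can show.

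**1. Markers (SAP 3.2.1 against 12.2, item 2).**
- With data: CXCL9, CXCL10, IFNγ V-PLEX, total IFNγ, sIL2Rα, IL-1β, IL-6, IL-10, TNFα, neopterin and sCD163. That is 11 assays of 10 analytes.
- In item 2: CXCL9, CXCL10, IFNγ and sIL2Rα. That is 4 analytes, or 5 assays if IFNγ means both.
- Left out: 10 − 4 = 6 analytes. If only one IFNγ assay is meant, 11 − 4 = 7 assays are left out. The text does not say which is intended.

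**2. Marker-by-laboratory pairs.** SAP 3.2.2 names 25 laboratory variables, with the differential counted once besides basophils.
- Planned: 5 × 25 = 125.
- All assays: 11 × 25 = 275.
- Not planned: 6 × 25 = 150, and 150/275 = 54.5%.

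This measures scope, not harm; most of these pairs are not needed.

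**3. Where the six markers still appear.**
- SAP 12.1: plotted and summarised by HLH and non-HLH group.
- SAP 12.2, item 1: 11 × 10/2 = 55 marker pairs. The five item 2 assays form 5 × 4/2 = 10 pairs among themselves, so 55 − 10 = 45 pairs involve at least one of the six. These include plots against sIL2Rα (sCD25), which the protocol lists as an HLH-2004 criterion.
- SAP section 8: individual listings.

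Only their plots against the 3.2.2 laboratory list are missing.

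**4. Precision of one correlation.** Inputs: n = 19 M-HLH patients (SAP section 6) and an assumed r. The 95% interval is tanh(atanh(r) ± 1.96/√(n − 3)).
- r = 0.5: 0.549 ± 1.96/√16 = 0.549 ± 0.490, so 0.06 to 0.78.
- r = 0.7: 0.867 ± 0.490, so 0.36 to 0.88.

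The three-day matching window (12.2) and the absence of imputation (8.1) make 19 a ceiling. The SAP plans scatter plots, not coefficients, so the interval only indicates how much such a plot can carry.

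**5. Telling two markers apart.** Simulation from a trivariate normal distribution, n = 19, 20,000 runs. All correlations are assumptions.

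| Marker A with lab value | Marker B with same lab value | A with B | Middle 95% of observed difference |
|---|---|---|---|
| 0.6 | 0.4 | 0.5 | −0.19 to 0.62 |
| 0.7 | 0.4 | 0.5 | −0.05 to 0.71 |
| 0.7 | 0.3 | 0.3 | −0.03 to 0.87 |
| 0.7 | 0.3 | 0.7 | 0.11 to 0.76 |

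Only the last case excludes zero. Comparator plots can show that a pattern is shared, but they separate markers only when differences are large.

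**6. Size of a short comparator panel.** Six markers against ferritin, platelets, AST and ALT: 6 × 4 = 24 extra plots. If item 2 was meant to use only one IFNγ assay, it is 7 × 4 = 28.

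**The case against.** The focus on the IFNγ axis fits the stated purpose. Both documents describe the study as one of IFNγ and IFNγ-inducible chemokines as markers of disease activity. In the protocol's background, the markers that "were found to significantly correlate with laboratory parameters of disease severity, such as ferritin, platelet count and transaminases" are IFNγ and its three chemokines. SAP 3.2.2 announces a selection, the SAP is to be signed before database lock, everything is exploratory, and no tests are presented. This stands as a reason to give the four markers the fuller analysis. It does not remove the other six from an objective that the SAP repeats unchanged, and a descriptive plan still has to address its objectives.

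A reader might infer that the six markers are lost from the study. They are not, as step 3 of the working shows.

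A reader might also infer that this omission is what prevents an IFNγ-specific relation from being told apart from general inflammation. The documents do not support that. Neither promises a specificity analysis. Partial comparators are planned: CRP is in the laboratory list, sIL2Rα is among the four and is not one of the chemokines that the protocol calls IFNγ-induced, and item 1 plots IFNγ against IL-6, IL-10 and TNFα. Adding the missing plots would not settle specificity in 19 patients either.

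Nor is there evidence that the four were chosen on results. The reason given is relevance to the product, which is consistent with the stated purpose.

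**Conclusion.** The point holds as one of completeness and transparency. Six of the ten measured analytes have no planned relation to any laboratory assessment in SAP 3.2.2, although objective 2 covers them and 12.2 opens without a restriction. Objective 2 is unanswered for them on those measures. The side-by-side view that would show whether an IFNγ-axis pattern is shared is missing. The narrowing is hinted at in 3.2.2 but not declared in section 14, and item 2 leaves the IFNγ assay unnamed.

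The point does not invalidate the planned analyses. The count of six rests only on the SAP's lists. The precision statements rest on assumed correlations, approximate normality (possibly after log transformation) and complete data in all 19 M-HLH patients, which is the best case.

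**What to change.** - **SAP 12.2, item 2:** add plots of all 11 assays in 3.2.1 against ferritin, platelets, AST and ALT, the severity parameters named in the protocol background, arranged so that markers can be compared for the same laboratory value. Name both IFNγ assays, V-PLEX and total. Keep the existing four-marker set against the full laboratory list.
- **SAP section 14:** record that the full laboratory list is used only for the four markers, and give the reason.
- **Interpretation:** state that these descriptive plots support no conclusion on IFNγ specificity.

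The cost is a few lines of text and 24 extra exploratory plots for the six markers, from data already measured, with no tests added. Since SAP 5.2 requires analyses outside the SAP to be labelled post hoc, the plots are better specified before the SAP is locked. If they are not added, section 14 should declare the restriction, and conclusions on objective 2 should be limited to the four markers.
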